#### Purpose

Word learning is one of the principal weaknesses in children with developmental language disorder (DLD). Our previous work has shown that special benefits accrue when these children must frequently recall newly introduced words during the course of learning. The focus of the current study is learning verbs. The goal of the study is to extend our findings on the benefits of retrieval practice by increasing children's absolute levels of verb learning while maintaining the advantage that repeated retrieval holds over comparison methods of learning. We include typically developing peers as a comparison group.

#### Participant selection

Preschool children with DLD are recruited through local speech-language pathologists and preschool teachers. Children with typical language development are recruited through advertisements in parent newsletters, preschools, and community events.

For interested families, a phone interview is used to screen for the following eligibility requirements:

- 1) current age between 4;0 and 5;11 (years; months)
- 2) monolingual English speaker; or bilingual speaker with significant English exposure from birth.
- 3) no significant neurological condition or neurodevelopmental disorder (e.g. ASD).

Informed consent is obtained at the first session and eligibility testing is then completed. To be eligible, the child must:

- 1) pass a pure tone hearing screening in both ears at 20 dB at 500, 1000, 2000, and 4000 Hz
- 2) score above 75 on a test of non-verbal intelligence (*Kaufman Assessment Battery for Children – Second Edition*).
- 3) complete the *Structured Photographic Expressive Language Test – Preschool 2* and receive a standard score in the following range:
  - a. To be included in the DLD group, children had a standard score below 87. This cutoff score has been found to show good sensitivity and specificity (Greenslade et al., 2009).

- b. To be included in the TD group, children had a standard score above 87.

All children also complete the Peabody Picture Vocabulary Test – Fifth Edition. Parents complete a questionnaire that includes mother's total years of education. The PPVT standard scores and years of maternal education are both used as covariates in all statistical analyses.

For eligible children, 6 sessions are scheduled to complete the study.

#### Word learning procedure

In the current study, the investigators seek to improve the absolute levels of word form recall for verbs. Using a within-subjects design, children will learn eight novel verbs, four at a time. Each set of four will be learned over two consecutive days, with two words in the repeated spaced retrieval condition and two words in a repeated study condition, presented in alternating order. The referents for these novel words will be video-recorded transitive actions performed by actors on objects and presented on a laptop screen. The actors and objects used in these videos systematically vary to promote learning of the verb meaning. For each verb, there are two different agents combined with two different objects, creating 8 unique videos per verb. The novel words are monosyllabic (consonant-vowel-consonant) and are matched across conditions according to phonotactic probability and neighborhood density (based on Storkel & Hoover, 2010).

Two learning periods for each set are held on consecutive days. For novel verbs in the RSR condition, the first two retrieval trials are immediate retrieval trials. After viewing and listening to a study trial (e.g., "The woman is pumming the cow. That woman is pumming the cow"), the video is re-presented and the child is given the retrieval prompt ("What's happening here? The ..."). After this, all retrieval trials appeared after the other three novel verbs have intervened (these are the spaced retrieval trials). All retrieval trials—immediate and spaced— are directly followed by another study trial for the same novel verb. The novel verbs in the repeated study condition received the same kinds of study trials but no retrieval trials. The second day is identical to the first day except that the order of the items is changed. Across the two days, there are a total of 16 study trials for each novel verb and 12 retrieval trials (four immediate, eight spaced) for each novel verb in the RSR condition. The same number of study trials are provided for the novel verbs in the two conditions.

See [https://doi.org/10.1044/2024\\_JSLHR-24-00321](https://doi.org/10.1044/2024_JSLHR-24-00321) Appendix A and B for stimuli and learning schedules.

#### Outcome measures

Primary outcome measures:

Verb Recall measure at 5 minutes. For each set, after the child has completed the learning session of the second day, a five-minute break is given. Then a recall test of each verb is administered. The prompts for this 16-item test are the same used for the retrieval trials in the learning period ("What's happening here? The ...") to which the child would respond using the verb in a full sentence (e.g., The woman is pumming the frog). Each verb is tested with four items, two learned items and two generalization items (differing in actor or object of the verb). For this test, the verbs are presented in blocks of alternating item type (i.e., the verbs are first tested using learned items, then generalized items, followed by another block of learned, then generalized items).

Verb Recall measure at one week. One week after learning, the Verb Recall test is re-administered.

Verb Recall in a New Structure measure. After the one week recall test, the children are asked to use the novel verbs in a structure different from the one in which they learned the verb (i.e. The Noun likes to Verb the Noun). There are 16 items in this test, 4 for each verb. Two of the videos are familiar from the learning period; two differed from the learning period in choice of actor or object of the verb.

Verb Recognition measure. The third test administered at one week required the child to point to the video corresponding to a sentence they heard. There are four items per novel verb, half representing learned items and half representing generalization items.

Secondary outcome measures:

Peabody Picture Vocabulary Test – Fifth Edition is completed. Standard scores are obtained and used as a covariate in all statistical analyses.

Parents complete a questionnaire that includes mother's total years of education. Years of maternal education is used as a covariate in all statistical analyses.

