### Scoring

Verb Recall measure. Sixteen items are used for the word form recall test for each set. Items are scored based on accuracy of recalling the novel verb form and use of the target sentence structure.

Steps are used in the scoring of children's word forms:

- 1) Productions of real words alternatives to the novel word (e.g., "kicking") are scored as incorrect.
- 2) Productions that appear to be attempts at the novel word but are not accurate are submitted to the scoring system of Edwards et al. (2004). Each consonant is awarded one point each for correct place, manner, and voicing. For vowels, one point is given for each of length, height, and backness. An additional point is credited for correct syllable shape (CVC). Given that all novel words had the syllable shape CVC, all fully adult-like pronunciations earned 10 points. For any non-adult-like production to be scored as correct, the production is required to have a higher point total than the total that would be given if the child is instead trying to produce one of the other novel words.

Criteria for correct use of the target sentence structure is production of the subject/agent noun, the correct novel verb inflected with *-ing*, and the object/patient noun (e.g., "Woman pumming the cow"). Allowances are made if the children used the wrong noun if the error constituted a reasonable misidentification. Because many children with DLD in this age range are inconsistent in their use of auxiliary *is*, inclusion of this grammatical morpheme is not required.

Verb Recall in a New Structure measure:

To be scored as correct, the response had to include the subject/agent noun, the verb *like*, and the correct novel verb in bare stem form (e.g., "Man like to pum the frog"). The grammatical morphemes present third person singular *-s* and infinitival *to* are used inconsistently by children with DLD at this age (Leonard, 2014) and are therefore not required.

Verb Recognition measure: Sixteen items are used for the verb recognition test.

The child's picture pointing response is recorded at the time of test. The score for the recognition test is the number of items in which the child pointed to the correct video in a two-video pairing.

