#### *Data analysis plan*

Mixed-effects models will be used to evaluate the children's responses on the verb recall measure, the verb recall in a new structure measure, and the verb recognition test. Models will be run with and without the covariates of PPVT-5 and maternal education in years. The number of items correct is the outcome measure for each analysis. The verb recall test is administered five minutes after the learning period and one week later. For this test, diagnostic group (DLD, TD) is a between-participants variable and learning condition (RSR, repeated study), time (five minutes, one week), and item type (learned, generalized) are within-participants variables. The verb recognition test is administered only at the one-week mark and therefore did not include time as a variable. The verb recall in a new structure test, also administered only one week later, required the children to use a sentence structure not used during the learning period, so neither item type nor time is included in the analysis. We included random slopes for learning condition, item type, and time when they did not approach zero.

Main-effects models and full factorial models with all possible interactions will be tested hierarchically. The main-effects models are presented initially with no interactions to provide a baseline of each model variable. Statistically significant interactions are then presented and relevant simple effects are reported. Effect sizes are presented as partially standardized beta coefficients ( $b_{std}$ ). These are comparable to  $d$ , though they reflect conditional standardized mean differences conditioned on other variables in the model. To account for non-normal error terms, we used boot-strapped standard errors with 1,000 replicates. Stata Version 18.0 (StataCorp, 2023) is used for the mixed-effect model analyses.

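### Verb Recall is described only in a learned-generalized-learned-generalized block order, so item type is partly confounded with test position (mean block 2 against 3)

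*Combined protocol and SAP*

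**What the plan says.** The Outcome measures section describes Verb Recall as a 16-item test per word set: "Each verb is tested with four items, two learned items and two generalization items". The items are grouped by type, and the order is stated once: "the verbs are first tested using learned items, then generalized items, followed by another block of learned, then generalized items". The later test is the same instrument: "One week after learning, the Verb Recall test is re-administered". Neither section describes a reversed, randomized or counterbalanced block order. The only change of order mentioned anywhere is for the items on the second learning day (Word learning procedure). The external appendices are cited there for stimuli and learning schedules, not for test order.

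In the Data analysis plan, "item type (learned, generalized) are within-participants variables" alongside learning condition and time, and the full factorial model tests every interaction. The response is a count: "The number of items correct is the outcome measure for each analysis". No block or position term is listed.

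**The concern.** With one fixed order, every Verb Recall test at both time points begins with a learned block and ends with a generalized one. Alternation reduces the imbalance but does not remove it, and adding children or word sets in the same order will not average it away.

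Two kinds of trend are plausible. Each test item repeats the prompt used for retrieval in training, and the study's premise is that retrieval helps, so later blocks could gain from earlier ones. Children aged four and five giving 16 full-sentence responses could also tire. Practice would flatter generalized items and could hide a real generalization deficit; fatigue could produce a spurious one.

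The contrast at stake is recall with new actors or objects against recall with learned ones, within a primary outcome. The item-type interactions are exposed only if the trend differs by condition, group or time. The Word learning procedure section gives one reason it might differ by condition: "The novel verbs in the repeated study condition received the same kinds of study trials but no retrieval trials". Verbs from the two conditions therefore enter the test with very different amounts of prior prompting.

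**Working it through.** **Inputs.** Two sets of four verbs, two per condition in each set, and 12 retrieval trials per RSR verb (Word learning procedure); four items per verb, two of each type, and the block order (Outcome measures); 16 items per test (Scoring). The documents give no trend within the test, so d and s below are symbols or labelled assumptions.

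**Plan's own figure.** 4 verbs × 4 items = 16, as stated. With four blocks this implies four items per block, taken here as one per verb.

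**Position by item type.**
- Learned: mean block (1 + 3)/2 = 2. Generalized: (2 + 4)/2 = 3.
- Earlier test prompts for the same verb: learned (0 + 2)/2 = 1; generalized (1 + 3)/2 = 2.
- Of the four learned-generalized block pairs (1-2, 1-4, 3-2, 3-4), the learned block comes first in three.
- Correlation of item type with block: 0.447. An unalternated order (learned, learned, generalized, generalized) would give 0.894 and a gap of 2 blocks instead of 1.

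**Bias under a linear trend of d per block.** Generalized minus learned is shifted by 3d − 2d = d. Items per condition, item type and time: 2 sets × 2 verbs × 2 items = 8. Assumed d of 0.02 gives 0.02 × 8 = 0.16 items; assumed d of 0.05 gives 0.05 × 8 = 0.40 items.

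**Can the existing order separate a linear trend?** Yes, because blocks 1 and 3 share an item type, as do 2 and 4. With block means y1 to y4:
- Trend estimate: ((y3 − y1) + (y4 − y2))/4, which has expectation d.
- Raw contrast weights: (−1/2, 1/2, −1/2, 1/2). Subtracting the trend estimate gives (−1/4, 3/4, −3/4, 1/4).
- Sums of squared weights: raw 1; adjusted (1 + 9 + 9 + 1)/16 = 1.25. The variance inflation is 1.25 and the standard error ratio √1.25 = 1.118, assuming independent block errors. This agrees with 1/(1 − 0.447²) = 1.25.

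A count pooled over the two blocks of each type discards the information needed for this.

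**If the trend is not linear.** Suppose only block 1 is lower, by s. The raw bias is s/2, the trend estimate is s/4, and the adjusted bias is s/2 − s/4 = s/4. With one set reversed, the biases are +s/2 and −s/2 and average to 0.

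**Trend that differs by condition.** At five minutes, repeated-study verbs enter blocks 1 to 4 with 0, 1, 2 and 3 earlier prompts; RSR verbs enter with 12, 13, 14 and 15. If the linear trends differ, the condition-by-item-type term is biased by their difference; if they are equal, by 0.

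**The case against.** The strongest objection is about importance. The Purpose section is concerned with how much children learn and with the advantage of retrieval over comparison methods. It does not mention item type, and the analysis plan states no hypothesis about it. If each verb is tested once per block, both conditions occupy the same blocks, so a common trend cancels in the RSR comparison, both overall and within generalized items alone. That stands, and it limits the concern to the item-type effect and its interactions.

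The size and sign of any trend are also unknown; practice and fatigue oppose each other, and the prompt counts do not prove that trends differ by condition. This stands too: the documented fact is a one-block imbalance, and the percentage points are assumed.

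Reversing the order has a price, since half the tests would open with a generalized item, and carryover that differs between the two directions would not cancel. Linear adjustment leaves half the bias if only block 1 differs. Both points are correct.

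The 12% figure is an upper value under this plan. With item-type slope variance t² and block-error variance e², the variance goes from t² + e² to t² + 1.25e². If t² = e² (assumed), the standard error rises by √(2.25/2) − 1, about 6%. This makes adjustment cheaper.

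None of this removes the imbalance, and item type remains a planned factor for a primary outcome.

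**Conclusion.** The concern holds. In the only order described, item type and test position are partly confounded, and the planned model does nothing to separate them. The item-type contrast is biased by d for a linear trend of d per block, or by s/2 if only the first block is lower by s. The documents do not let d or s be estimated; the range of 0.16 to 0.40 items out of 8 rests on an assumed 2 to 5 points per block. The learning-condition and group main effects are safe from a trend common to all verbs and children, given one item per verb in each block. The conclusion also assumes that no counterbalancing was used beyond what is written. It applies to Verb Recall only: Verb Recognition has both item types but no stated block order, and item type is not analysed in the new-structure test. The change is worth making because it is cheap, not because the main question is threatened.

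**What to change.** **Before testing.** Use learned-generalized-learned-generalized for one word set and generalized-learned-generalized-learned for the other, with the assignment swapped for half the children, at both five minutes and one week. Each item type then occupies every block, and any common additive block effect cancels. Keep scores at block or item level and include block position in the recall model. The cost is reordered test slides and an assignment list, with no extra testing time; the drawback is that half the tests begin with a generalized item.

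**If testing is complete** (the plan mixes tenses, so this is unclear). Rebuild the scores at block or item level and add a linear block term as a sensitivity analysis. A common block term does not protect the condition-by-item-type interaction; for that, let the term differ by condition. Report accuracy by block for each condition and group, so that readers can see whether a trend exists, and state the limitation beside the Verb Recall item-type result. The cost is reanalysis only, with a standard error for the item-type contrast about 12% larger under independent block errors and a common linear term, and less if item-type effects vary between children.

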### Scoring

Verb Recall measure. Sixteen items are used for the word form recall test for each set. Items are scored based on accuracy of recalling the novel verb form and use of the target sentence structure.

Steps are used in the scoring of children's word forms:

- 1) Productions of real words alternatives to the novel word (e.g., "kicking") are scored as incorrect.
- 2) Productions that appear to be attempts at the novel word but are not accurate are submitted to the scoring system of Edwards et al. (2004). Each consonant is awarded one point each for correct place, manner, and voicing. For vowels, one point is given for each of length, height, and backness. An additional point is credited for correct syllable shape (CVC). Given that all novel words had the syllable shape CVC, all fully adult-like pronunciations earned 10 points. For any non-adult-like production to be scored as correct, the production is required to have a higher point total than the total that would be given if the child is instead trying to produce one of the other novel words.

Criteria for correct use of the target sentence structure is production of the subject/agent noun, the correct novel verb inflected with *-ing*, and the object/patient noun (e.g., "Woman pumming the cow"). Allowances are made if the children used the wrong noun if the error constituted a reasonable misidentification. Because many children with DLD in this age range are inconsistent in their use of auxiliary *is*, inclusion of this grammatical morpheme is not required.

Verb Recall in a New Structure measure:

To be scored as correct, the response had to include the subject/agent noun, the verb *like*, and the correct novel verb in bare stem form (e.g., "Man like to pum the frog"). The grammatical morphemes present third person singular *-s* and infinitival *to* are used inconsistently by children with DLD at this age (Leonard, 2014) and are therefore not required.

Verb Recognition measure: Sixteen items are used for the verb recognition test.

The child's picture pointing response is recorded at the time of test. The score for the recognition test is the number of items in which the child pointed to the correct video in a two-video pairing.

#### *Data analysis plan*

Mixed-effects models will be used to evaluate the children's responses on the verb recall measure, the verb recall in a new structure measure, and the verb recognition test. Models will be run with and without the covariates of PPVT-5 and maternal education in years. The number of items correct is the outcome measure for each analysis. The verb recall test is administered five minutes after the learning period and one week later. For this test, diagnostic group (DLD, TD) is a between-participants variable and learning condition (RSR, repeated study), time (five minutes, one week), and item type (learned, generalized) are within-participants variables. The verb recognition test is administered only at the one-week mark and therefore did not include time as a variable. The verb recall in a new structure test, also administered only one week later, required the children to use a sentence structure not used during the learning period, so neither item type nor time is included in the analysis. We included random slopes for learning condition, item type, and time when they did not approach zero.

Main-effects models and full factorial models with all possible interactions will be tested hierarchically. The main-effects models are presented initially with no interactions to provide a baseline of each model variable. Statistically significant interactions are then presented and relevant simple effects are reported. Effect sizes are presented as partially standardized beta coefficients ( $b_{std}$ ). These are comparable to  $d$ , though they reflect conditional standardized mean differences conditioned on other variables in the model. To account for non-normal error terms, we used boot-strapped standard errors with 1,000 replicates. Stata Version 18.0 (StataCorp, 2023) is used for the mixed-effect model analyses.

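### The adjusted DLD versus TD comparison has no age term, although outcomes are raw item counts from non-randomised groups spanning two years of age

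*Combined protocol and SAP*

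**What the plan says.** The Data analysis plan gives the covariates in one sentence: "Models will be run with and without the covariates of PPVT-5 and maternal education in years". Participant selection names the same two: "The PPVT standard scores and years of maternal education are both used as covariates in all statistical analyses". Outcome measures confirms the scale of the PPVT-5: "Standard scores are obtained and used as a covariate in all statistical analyses". Age is not a covariate in any of the three places.

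Age appears only as an eligibility criterion checked at the phone interview: "current age between 4;0 and 5;11 (years; months"). The same window applies to both groups. Children are then classed as DLD or TD by their standard score on the expressive language test, and the two groups are recruited by partly different routes. Neither section mentions matching or stratifying on age, or reporting age by group. The Purpose section calls the TD children peers but does not define that by age.

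On the models, the Data analysis plan states that "diagnostic group (DLD, TD) is a between-participants variable" and that "The number of items correct is the outcome measure for each analysis". It adds that "full factorial models with all possible interactions will be tested hierarchically", so interactions between group and learning condition are also tested. The retrieval comparison itself is made within each child: "Using a within-subjects design, children will learn eight novel verbs, four at a time", with both learning conditions in each set of four.

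**The concern.** A raw count of novel verbs recalled or recognised may well rise with age between 4;0 and 5;11. Nothing in the design makes the two groups equal in age, because they are not randomised and no matching is stated. The adjusted model is where a reader would expect such a difference to be handled, and its two covariates do not handle it. An age-normed standard score expresses a child's vocabulary relative to children of the same age, so it carries little information about age itself. Maternal education carries none in any obvious way.

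Three estimates need to be kept apart:

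- **Group main effect.** If the DLD children are on average younger, the adjusted deficit is overstated. If they are older, it is understated.
- **Group-by-condition interaction.** This is distorted only if the groups differ in age and the retrieval advantage also changes with age.
- **Average retrieval effect.** Age is constant within a child, so this effect is not confounded by age.

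If mean ages happen to be equal there is no bias, but age-related spread stays in the between-child variance and the group standard error is somewhat larger than it need be.

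**Working it through.** The documents give no sample size, age distribution or age-score correlation, so there is no figure of the plan's own to reproduce. What follows shows the size under stated assumptions.

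**Inputs**
- From the documents: an age window of 4;0 to 5;11, about 24 months (Participant selection); raw counts, group between children and two covariates (Data analysis plan); PPVT-5 as a standard score (Outcome measures).
- Assumed: age uniform over the window; within-group correlation r between age and the child's mean score of 0.3 to 0.5; covariates unrelated to age within group; equal group sizes.

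**Spread of age.** SD = 24/√12 = 6.93 months. A gap in mean age of g months is d = g/6.93, so d = 0.433 for 3 months and 0.866 for 6 months.

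**Shift in the group effect when age is omitted.** Shift = r × d, in within-group SDs of the child's mean score.

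| Gap in mean age | r = 0.3 | r = 0.5 |
|---|---|---|
| 0 months | 0 | 0 |
| 3 months | 0.3 × 0.433 = 0.13 | 0.5 × 0.433 = 0.22 |
| 6 months | 0.3 × 0.866 = 0.26 | 0.5 × 0.866 = 0.43 |

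**Simulation check.** With 4,000 replicates, 20 per group, a PPVT slope of 0.3, a PPVT group gap of 0.8 SD, a 3-month age gap and a true adjusted group effect of 0, the PPVT-adjusted model gave 0.128 (r = 0.3) and 0.221 (r = 0.5). Adding age gave -0.003 and 0.001. A separate large-sample run (200,000 per group) included both planned covariates, with DLD children 3 months younger, an age slope of 0.4 per SD of age and a true group effect of -0.50. It gave -0.67 without age and -0.50 with age. The within-child retrieval contrast in that run was 0.60, its true value.

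**Effect on the group standard error.** The ratio with age to without age is √(1 − r²) × √(1 + d²/4).

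| Gap | r = 0.3 | r = 0.5 |
|---|---|---|
| 0 months | 0.954 (-5%) | 0.866 (-13%) |
| 3 months | 0.976 (-2%) | 0.886 (-11%) |
| 6 months | 1.040 (+4%) | 0.944 (-6%) |

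The ratio reaches 1 at a gap of 2 × 6.93 × √(1/(1 − r²) − 1), which is 4.4 months for r = 0.3 and 8.0 months for r = 0.5.

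**Gap expected by chance.** With n per group, the SE of the mean age difference is 6.93 × √(2/n). The 95% range is about ±5.0, ±4.3 and ±3.5 months for an assumed n of 15, 20 and 30.

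**Group-by-condition term.** If the retrieval advantage correlates 0.2 with age (assumed), a 3-month gap shifts this term by 0.2 × 0.433 = 0.09 SD of the child-level difference. Simulation gave 0.087 and 0.092, and 0.00 once an age-by-condition term was added. The overall condition effect came back at 0.50 against a true 0.50.

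**The case against.** No bias is shown. Both groups share one age window. Classification uses standard scores; if these are age-normed like the PPVT-5, classification does not itself create an age gap. Preschools feature in both recruitment routes, and nothing suggests that either favours older or younger children. This stands, and it is why the point is a gap in the plan and not an error in a result.

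The larger illustrated gaps are unlikely by chance. At an assumed 20 per group the SE of the gap is 6.93 × √(2/20) = 2.19 months, so a gap of 3 months or more has probability about 0.17 and one of 6 months or more about 0.006. The 6-month row therefore needs a systematic recruitment difference and should carry little weight. The 3-month row does not need one.

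The scale may also overstate the shift. The plan reports partially standardised coefficients without naming the SD. If it is the SD of single observations, the shift shrinks by √(ICC + (1 − ICC)/8) over the eight recall cells (condition × time × item type). For an assumed ICC of 0.3 to 0.7 that factor is 0.62 to 0.86, and the 3-month shift becomes 0.08 to 0.11 (r = 0.3) or 0.13 to 0.19 (r = 0.5). This is a fair caution; it reduces the shift without removing it.

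Finally, the main aim is untouched, and choosing covariates for a diagnostic comparison is partly judgement. Both are true. They bear on priority, but they are not a reason to leave out a baseline variable that is already ascertained.

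**Conclusion.** The concern holds. Neither the covariate list nor the recruitment plan deals with age, and an age-normed vocabulary score does not substitute for it. Under the assumed uniform age spread and r of 0.3 to 0.5, a 3-month difference in mean age, which is plausible by chance in groups of about 20, would move the adjusted DLD versus TD effect by 0.13 to 0.22 SD of the child's mean score, or somewhat less on an observation-level scale. With no age difference the cost is precision only: the group standard error would be 5% to 13% smaller with age in the model. Precision is not guaranteed to improve, since at r = 0.3 the gain is gone beyond a gap of about 4.4 months. The group-by-condition interaction is exposed only under the further assumption that the retrieval benefit varies with age. The average retrieval effect is sound. This is a change the plan should make, but it does not threaten the main aim.

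**What to change.** 1. In the Data analysis plan, define the covariate set for the adjusted models that contain group as PPVT-5, maternal education in years, and age in months at the first session. Keep the planned models without covariates unchanged.
2. Carry the same covariate list into Participant selection and Outcome measures.
3. Report mean, SD and range of age by group, so that readers can judge both the adjusted and the unadjusted group effects.
4. For the group-by-condition interaction, add a sensitivity model with an age-by-condition term. The same device applies to group interactions with time or item type if these will be interpreted.
5. Parts of the Data analysis plan are written in the past tense. If results have already been seen, label the age-adjusted models as added afterwards.

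The cost is one degree of freedom in the adjusted models and one more in the sensitivity model. Age is already ascertained at screening, so only the wording of the plan changes.
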